## 7.4. Exploratory Efficacy Analyses

No statistical testing is planned for exploratory endpoints, unless otherwise noted.

### 7.4.1. Planned Exploratory Efficacy Display Details

*Relationships between Daprodustat Exposure Parameters and Selected Efficacy Endpoints*

Endpoint / Variables	
Daprodustat Efficacy Dose Parameters	
Avg Dose EP TIR	The average TIW daprodustat dose when the subject is on-treatment and in target Hgb range during the evaluation period (EP) Weeks 28-52. Evaluable Hgb values are used to determine time in range. Subjects who permanently stop study treatment before the beginning of the EP, and subjects who have 0% time in range (e.g., subjects who have an evaluable Hgb below or above range for the entire EP) will have a missing value for this parameter
Avg Dose EP	The average TIW daprodustat dose when the subject is on-treatment during the EP.
Avg Dose 52	The average TIW daprodustat dose when the subject is on-treatment over 52 weeks
Daprodustat Efficacy Special Parameters	
Cmax/1mg Dose	Cmax extrapolated to 1mg dose: Observed Cmax divided by dose administered on the PK day
Cmax/Avg Dose EP TIR	Cmax extrapolated to average dose during EP TIR: Cmax/1mg multiplied by the average TIW daprodustat dose when the subject is on-treatment and in target Hgb range during Weeks 28-52. Evaluable Hgb values are used to determine time in range.
Cmax/Avg Dose EP	Cmax extrapolated to average TIW dose during EP: Cmax/1mg multiplied by the average TIW daprodustat dose during the EP.
Planned Exploratory Displays	

 
Scatter plot of % Time Evaluable Hgb in Range during EP vs. Cmax/Avg Dose EP TIR
 
Scatter plot of Mean Evaluable Hgb Change from Baseline during EP vs. Cmax/Avg Dose EP
 
Scatter plot of % Time Evaluable Hgb in Range during EP vs. Avg Dose EP TIR
 
Scatter plot of Mean Evaluable Hgb Change from Baseline during EP vs. Avg Dose 52
 
 
Daprodustat Efficacy Dose parameters (Avg Dose EP TIR, Avg Dose EP, Avg Dose 52) will be summarized using mean, standard deviation, minimum, P25, median, P75, and maximum. Efficacy Special parameters (Cmax/1mg Dose, Cmax/avg Dose EP TIR, Cmax/avg Dose EP,) will be summarized using mean, standard deviation, minimum, median, maximum, geometric mean, standard deviation of log-transformed data, and %CVb. A listing of the Efficacy Dose parameters and a listing of the Efficacy Special parameters will be provided.
	

*Hgb Variability*

Endpoint/Variables

 
• Hgb observed and change from baseline across all visits
 
• % of time Hgb is above, within and below the analysis range of 10 to 11.5 g/dL during the EP
 
• Number (%) of participants with mean Hgb above, within and below the Hgb analysis range during the EP
 
• Number (%) of participants with a Hgb <7.5 g/dL during the EP
 
• Number of times Hgb <7.5 g/dL during the EP
 
• Number (%) of participants with a >1 g/dL increase in Hgb within any 2-week period (assessed at Week 2 through Week 8), or with a >2 g/dL increase in Hgb within any 4-week period up to Week 52
 
• Number (%) of participants with a >1 g/dL decrease in Hgb within any 2-week period (assessed at Week 2 through Week 8), or with a >2 g/dL decrease in Hgb within any 4-week period up to Week 52
 
• N (%) of participants with a Hgb value <math>\geq 12</math> g/dL during the EP
 
• Number of times Hgb <math>\geq 12</math> g/dL during the EP
 
• % of time Hgb <math>\geq 12</math> g/dL during the EP
 

Planned Exploratory Displays

 
• All available Hgb values (on and off-treatment) will be summarized using mean, standard deviation, minimum, P25, median, P75 and maximum at each visit by treatment group (see Section 7.1.5). In addition to scheduled visits, the baseline value and mean EP and end of treatment values will be included (see Section 14.6.3).
 
• All available Hgb change from baseline values (on and off-treatment) will also be summarized using mean, standard deviation, minimum, P25, median, P75, and maximum at each post-baseline visit (see Section 7.1.5), including the mean EP and end of treatment values (see Section 14.6.3).
 
• The % time Hgb is above, within and below the Hgb analysis range (10-11.5 g/dL) during the EP will be summarized using mean, standard deviation, minimum, P25, median, P75, and maximum by treatment group (see Section 7.3.1). This summary will be presented using evaluable Hgb values only (see Section 14.6.3).
 
• Number (%) of participants with mean Hgb above, within and below the Hgb analysis range during the EP will be summarized by treatment group (see Section 7.3.1). This summary will be presented using evaluable Hgb values only (see Section 14.6.3)
 
• The number and percentage of subjects with a Hgb value < 7.5g/dL and the number of times a Hgb value < 7.5 g/dL occurs during the EP will be summarized by treatment group using central laboratory Hgb values and separately using HemoCue Hgb values. This summary will be presented using evaluable Hgb values only (see Section 14.6.3). The central laboratory summary will be considered the primary summary of this data.
 

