10.3.3.3. Other Exploratory Analyses

The exploratory graphics described below will be created.

- Scatter plots of mean weekly daprodustat dose over the EP vs. the percent time within the Hgb target range during the EP
- Scatter plots of mean weekly three-times weekly daprodustat dose over 52 weeks vs. mean Hgb over the 52-week treatment period
- Boxplots of mean weekly three-times weekly daprodustat dose, while on study treatment for participants without MACE, and before the event for participants with MACE or combined safety endpoint
- Boxplots of Cmax of three-times weekly dosed daprodustat extrapolated to daprodustat dose at PK sample multiplied by the daprodustat dose at the time of MACE or combined safety endpoint (or end of study if no endpoint) by participants with or without MACE or combined safety endpoint

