
 
The scenarios outlined below provide guidance on the use of unscheduled Hgb values and multiple Hgb values occurring on the same date. Each row represents a single calendar date.
 
Rows outlining scenarios where there is at least one central lab Hgb and at least one HemoCue Hgb on the same date apply only for the derivation of Hgb values to be used in the primary Hgb analysis, where central lab values are used if they are available and if the central lab value is missing, then a corresponding non-missing HemoCue Hgb value is used.
 
Rows outlining scenarios involving combinations of scheduled and unscheduled Hgb values of the same type apply to all Hgb summaries and analysis.
 
					
Scheduled Central Lab Hgb Value	Unscheduled Central Lab Hgb Value	Scheduled HemoCue Hgb Value	Unscheduled HemoCue Hgb Value	Value to Use	Type/Label
x				Scheduled central lab Hgb value	Scheduled visit
	x			Unscheduled central lab Hgb value	Unscheduled
		x		Scheduled HemoCue Hgb value	Scheduled visit
		multiple 		Average of scheduled HemoCue Hgb values	Scheduled visit
			x	Unscheduled HemoCue Hgb value	Unscheduled
	multiple			Average of unscheduled central lab Hgb values	Unscheduled

CONFIDENTIAL

204837

Hemoglobin Values					
			multiple	Average of unscheduled HemoCue Hgb values	Unscheduled
x	x			Average of central lab Hgb values	Scheduled visit
x		x		Scheduled central lab Hgb value	Scheduled visit
x			x	Scheduled central lab Hgb value	Scheduled visit
	x	x		Unscheduled central lab Hgb value	Unscheduled
	x		x	Unscheduled central lab Hgb value	Unscheduled
		x	x	Average of HemoCue Hgb values	Scheduled visit

1: The dose adjustment algorithm will require sites to obtain two HemoCue Hgb values at some visits.

Time In Range
Time in Range During the EP

 
Number of days that a subject's evaluable Hgb is within the analysis range of 10-11.5 g/dL inclusive during the EP (See Section 14.6.1), including any unscheduled evaluable Hgb values that were taken during this time period.
 
Use of unscheduled Hgb values follows the scenarios for unscheduled and multiple Hgb values.
 
Linear interpolation is used to estimate Hgb between visits, accounting for any intermittent missing values (Rosendaal, 1993).
 

Percent Time in Range During the EP

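### The two exploratory plots of % time in range use a dose averaged only over in-range time, which makes exposure depend on the outcome and drops every participant at 0%

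*SAP*

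**What the plan says.** SAP 7.4.1 defines Avg Dose EP TIR as "The average TIW daprodustat dose when the subject is on-treatment and in target Hgb range during the evaluation period (EP) Weeks 28-52". Participants who stop treatment before the EP have no value. The same holds for those never in range: "subjects who have 0% time in range (e.g., subjects who have an evaluable Hgb below or above range for the entire EP) will have" no entry for this dose. The Cmax version is built on the same dose: "Cmax extrapolated to average dose during EP TIR: Cmax/1mg multiplied by the average TIW daprodustat dose when the subject is on-treatment and in target" (that is, in range during the EP).

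These variables form the x-axis of both plots with time in range as the outcome: "Scatter plot of % Time Evaluable Hgb in Range during EP vs. Cmax/Avg Dose EP TIR" (Figure 2.036) and "Scatter plot of % Time Evaluable Hgb in Range during EP vs. Avg Dose EP TIR" (Figure 2.038). The figure list in SAP 14.10.7 has no programming note that alters this.

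The protocol planned the dose plot differently. Section 10.3.3.3 has "Scatter plots of mean weekly daprodustat dose over the EP vs. the percent time within the Hgb target range during the EP", and 10.3.3.2 scales Cmax by mean dose during the EP. Neither restricts to in-range time.

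SAP 14.6.3.1 defines time in range as days on which "evaluable Hgb is within the analysis range of 10-11.5 g/dL inclusive during the EP". SAP Table 1 lists the new PK-related parameters and gives transparency about intermediate endpoints as the reason.

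**The concern.** A plot of Hgb control against exposure should show where control failed as well as where it succeeded. Here the exposure value exists only if control succeeded at least some of the time, and it ignores doses given while Hgb was out of range. Under Protocol Table 7, low or high Hgb is what triggers dose steps, and a confirmed Hgb of 12 g/dL or more triggers an interruption. The discarded time is therefore when dose is most likely to be moving.

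Participants below or above range for the whole EP vanish from both figures, so control looks better than it was. Protocol 10.3.3.2 says that post-hoc exposure-response modelling may follow from these graphics together with the efficacy and safety results, so a truncated picture could influence what is modelled.

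**Working it through.** The documents state no figure for these plots that could be reproduced. The check is a comparison of definitions, followed by an illustration of size.

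**1. Exposure variable by source (outcome: % time in range during the EP)**

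| Source | Dose on the x-axis |
|---|---|
| Protocol 4 and SAP 2.2 (objectives tables) | Mean weekly dose over 52 weeks; extrapolated Cmax with no period named |
| Protocol 10.3.3.2 | Cmax scaled by mean weekly dose during the EP |
| Protocol 10.3.3.3 | Mean weekly dose over the EP |
| SAP 7.4.1, Figures 2.036 and 2.038 | Cmax scaled by, or directly, dose over in-range EP time only |

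Only the last row conditions on being in range. SAP 7.4.1 also defines Avg Dose EP and Cmax/Avg Dose EP without that condition, but uses neither for time in range.

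**2. Is 0% a defined outcome?** SAP 14.6.3.1 requires treatment to continue past the Week 28 visit and two evaluable Hgb values on different days, at least one of them in the EP. Someone who meets this and is never in range has zero days over a positive denominator, which is 0%. Those who stop before the EP have no outcome value anyway, so the avoidable loss is the 0% group.

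**3. How x depends on y.** Let T_in be in-range days and T_EP the on-treatment EP days. Then y = T_in / T_EP and x = (sum of dose over in-range days) / T_in. The numerator of y is the denominator of x. At T_in = 0, x does not exist; near 0, x rests on a few days.

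**4. Effect on the outcome axis.** Those dropped all sit at 0, so if a fraction z is dropped and the mean over everyone is m, the mean among those plotted is m / (1 − z). The relative inflation is 1/(1 − z) − 1: 2% at z = 0.02, 5% at 0.05, 18% at 0.15, 19% at 0.16 and 30% at 0.23.

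**5. Illustrative size of z.** Assumptions, none from the documents: mean EP Hgb 10.5 g/dL, within-person SD 0.5 to 0.8, correlation 0.5 between successive visits. Each scenario has 7 EP visits, linear interpolation and 20,000 simulated participants.

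| Between-person SD (g/dL) | At 0% in 10-11.5 |
|---|---|
| 0.4 | about 2% |
| 0.6 to 0.8 | 5 to 15% |
| 1.0 | 16 to 23% |

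Mean time in range among those kept exceeds that in all by 1 to 2 percentage points at SD 0.4, and by about 3 to 15 points over SD 0.6 to 1.0.

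For scale, the planned daprodustat arm is 268. With the protocol's allowance of 10% without EP Hgb, 268 × 0.9 ≈ 241. Two per cent of 241 is about 5 people, 5 to 15% is 12 to 36, and 16 to 23% is 39 to 55. Treatment discontinuation and missing PK samples would lower these counts.

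**6. Dose relation.** A second simulation added the protocol's dose steps with one-step titration and assumed that dose level falls as Hgb rises. Over eight scenarios (between-person SD 0.5 to 1.5) the Spearman correlation of dose with time in range was −0.29 to −0.17 with whole-EP dose and everyone kept. Under the SAP rule it was −0.22 to +0.01, nearer zero in all eight. This shows that the two plots can differ materially. It does not show which is closer to a true exposure effect, because the negative correlation was built in through titration.

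**The case against.** The strongest defence is that little rides on these plots. SAP 7.4 plans no testing of exploratory endpoints unless noted. Participants at 0% still count in the below/within/above summaries and in the van Elteren and responder analyses, and they can appear in the mean-Hgb plots (Figures 2.037 and 2.039). SAP 7.4.1 states the exclusion openly and Table 1 lists the parameters as new. All of that stands and limits the weight of the point. But the same Table 1 does explain the switch from mean Hgb to Hgb change from baseline, whereas transparency does not explain a different exposure variable.

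A second defence also stands in part: whole-EP dose is not free of the outcome either, since Protocol 7.2.3 titrates dose on Hgb throughout. Conditioning on in-range time adds a selection step to that problem; removing the step does not make the plot causal.

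Three stronger readings are tempting but unsupported:

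- *The dose parameter uses a 10.0-11.0 g/dL range, so a participant steady at 11.2 would have 100% time in range and no dose.* The titration target is 10.0-11.0, but the objectives tables and Protocol 10.3.3.2 and 10.3.3.3 use the target-range wording loosely for this same endpoint. The missing-value rule is tied to 0% time in range, which SAP 14.6.3.1 defines on 10-11.5. The wording needs clarifying; it does not establish a second exclusion.
- *The protocol has one variable to restore.* It does not: the objectives tables name 52-week dose and 10.3.3.3 names EP dose.
- *The exclusion could be 30 to 40%.* The simulation gives about that at a between-person SD of 1.5. The protocol's 1.5 g/dL, however, is a planning SD for change from baseline, not for the spread of evaluable EP Hgb around 10.5.

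**Conclusion.** The point holds on the text and needs no simulation: in Figures 2.036 and 2.038 exposure depends on the outcome and every participant at 0% is dropped. This departs from the whole-EP dose in Protocol 10.3.3.2 and 10.3.3.3 and is not presented as such.

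Its size is uncertain. It runs from about 2% to 23% of plotted participants over between-person SDs of 0.4 to 1.0 g/dL, under the assumed mean, within-person SD and correlation. A reader might infer that the rule hides or weakens a real exposure-response relation; the documents do not support that, because titration alone can produce the dose pattern. The defect is confined to two untested exploratory displays. It is worth correcting because it is cheap and because later modelling may draw on these figures.

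**What to change.** - In Figures 2.036 and 2.038, plot % time evaluable Hgb in the 10-11.5 g/dL analysis range against Cmax/Avg Dose EP and Avg Dose EP. Include all PK-population participants with a defined % time in range, 0% among them.
- If the in-range dose is still wanted, keep it as a labelled supplementary plot with a footnote counting those excluded below range and above range.
- Name the 10-11.5 g/dL range in the parameter definition.
- Record the change, with its reason, in SAP Table 1.
- Reconcile the 52-week dose in Protocol 4 and SAP 2.2 with the EP dose in Protocol 10.3.3.2 and 10.3.3.3.
- Add a note that dose is titrated on Hgb, so the plots are descriptive and not causal exposure-response.

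The cost is SAP wording and two figure programs. Both replacement parameters are already derived and summarised, and no new data are needed.

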**CONFIDENTIAL**

204837

- The number and percentage of subjects with a >1 g/dL increase in Hgb over 2 weeks (assessed at Week 2 through Week 8) or a >2 g/dL increase in Hgb within any 4-week period up to Week 52 will be summarized by visit and overall at Week 52 by treatment group using central laboratory Hgb values and separately using HemoCue Hgb values. This summary will be presented using evaluable Hgb values only (see Section 14.6.3). The central laboratory summary will be considered the primary summary of this data.
- The number and percentage of subjects with a >1 g/dL decrease in Hgb over 2 weeks (assessed at Week 2 through Week 8) or a >2 g/dL decrease in Hgb within any 4-week period up to Week 52 will be summarized by visit and treatment group using central laboratory Hgb values and separately using HemoCue Hgb values. This summary will be presented using evaluable Hgb values only (see Section 14.6.3). The central laboratory summary will be considered the primary summary of this data.
- The number and percentage of subjects with a Hgb value  $\geq 12$  g/dL and the number of times a Hgb value  $\geq 12$  g/dL occurs during the EP will be summarized by treatment group using central laboratory Hgb values and separately using HemoCue Hgb values. This summary will be presented using evaluable Hgb values only (see Section 14.6.3). The central laboratory summary will be considered the primary summary of this data.
- The percentage of time Hgb is  $\geq 12$  g/dL during the EP will be calculated using the Rosendaal method as described in Section 7.3.1. The percentage of time Hgb is  $\geq 12$  g/dL during the EP will be summarized using mean, standard deviation, minimum, P25, median, P75, and maximum by treatment group. This summary will be presented using evaluable Hgb values only (see Section 14.6.3). In addition, the percentage of time Hgb is  $\geq 12$  g/dL for subjects with at least one Hgb  $\geq 12$  g/dL during the EP will be summarized using mean, standard deviation, minimum, P25, median, P75, and maximum by treatment group calculated using evaluable Hgb values.

*Iron Parameters*

Endpoint / Variables

 
• Observed and change from baseline in hepcidin, ferritin, transferrin saturation (TSAT), total iron, total iron binding capacity (TIBC) across all visits
 
• Average quarterly ferritin
 
• Average quarterly TSAT
 
• Average quarterly IV iron dose/participant
 
• N (%) of participants who met iron management criteria
 
• N (%) of participants who reduced IV iron supplementation relative to baseline [defined as total iron (mg) over 4 weeks prior to randomization] during EP [defined as average monthly IV iron dose (mg) over Weeks 28 to 52]
 

Planned Exploratory Displays

 
• Hepcidin, ferritin and total iron on-treatment values will be log-transformed (see Section 5.2.2) and summarized using geometric mean, coefficient of variation, minimum, P25,
 

CONFIDENTIAL

204837

median, P75, and maximum for each scheduled visit by treatment group. Graphical summaries will be provided.

- TSAT, TIBC, and UIBC on-treatment values will be summarized using mean, standard deviation, minimum, P25, median, P75, and maximum for each scheduled visit by treatment group. Graphical summaries will be provided except for UIBC.
- Percent change from baseline in log-transformed (see Section 5.2.2) hepcidin, ferritin and total iron on-treatment values will be summarized using geometric mean, 95% CI, minimum, P25, median, P75, and maximum for each scheduled visit by treatment group. Graphical summaries will be provided.
- Change from baseline in TSAT, TIBC, and UIBC on-treatment values will be summarized using mean, standard deviation, minimum, P25, median, P75, and maximum for each scheduled visit by treatment group. Graphical summaries will be provided except for UIBC..
- Average quarterly IV iron dose/subject while on treatment will be summarized by presenting average monthly IV iron dose by quarter (see Section 14.6.3). Summaries will include mean, standard deviation, minimum, P25, median, P75, and maximum by treatment group. Graphical summaries will be provided.
- The number and percentage of subjects who used IV iron, oral iron and/or other iron while on-treatment will be summarized by quarter.
- Average quarterly TSAT while on treatment will be summarized by presenting average TSAT values for the quarters used to generate IV iron dose by quarter (see Section 14.6.3). Summaries will include mean, standard deviation, minimum, P25, median, P75, and maximum by treatment group. Graphical summaries will be provided.
- Average quarterly ferritin while on treatment will be summarized by presenting average ferritin values by quarter (see Section 14.6.3). Summaries will include geometric mean, coefficient of variation, minimum, P25, median, P75, and maximum by treatment group. Graphical summaries will be provided.
- The number and percentage of subjects that met the iron management criteria during the study while on treatment will be summarized by treatment group for each 3-month period of the study and across the entire study. There are two types of iron management thresholds: the first type requires that iron therapy be administered if subjects have ferritin and/or TSAT values that are too low; the second type requires that all iron (excluding multivitamins) must be stopped if ferritin and/or TSAT values are too high. It is also possible for a subject to meet starting and stopping criteria on the same day with a low ferritin and a high TSAT. These subjects will also be summarized (see Section 14.6.3). Assessment of meeting iron management thresholds will be made based on central laboratory data values. at the scheduled visits for ferritin and TSAT assessments, according to the schedule outlined in the Schedule of Activities table (see Section 14.2.1). Further, the subjects who met the threshold requiring iron administration to start or stop while on IV iron will be grouped by the action taken with IV iron therapy in the 8 weeks following the date the threshold was met (i.e., starting or increasing iron therapy, maintaining existing iron therapy, receiving no iron therapy, stopping or decreasing iron therapy with no increase, Section 14.6.3) according to concomitant medication records for IV iron.
- The number and percentage of subjects that reduced IV iron supplementation relative to baseline during the EP while on treatment will be summarized by treatment group (see Section 14.6.3).

- A stacked bar chart of on-treatment iron use will be created by treatment group to show the percentages of subjects with different types of iron use at baseline and at each quarter post-baseline.

### *RBC and Whole Blood Transfusions*

Endpoint / Variables

 
• Number (%) of participants who receive at least one RBC or whole blood transfusion by Week 52
 
• Number of RBC and whole blood transfusion events per 100 patient years
 
• Number of RBC and whole blood transfusions per 100 patient years
 
• Number of RBC and whole blood units per 100 patient years
 
• Time to first RBC and whole blood transfusion
 

Planned Exploratory Displays

 
• Summary and analysis tables will use the All Randomized (ITT) population.
 
• The total number of on-treatment RBC and whole blood transfusion events, transfusions and units for each subject will be derived as described in Section 14.6.3
 
• The number of on-treatment RBC and whole blood transfusion events per subject, the number of subjects with at least one RBC and whole blood transfusion event, and total number of RBC and whole blood transfusion events will be summarized.
 
• The number of on-treatment RBC and whole blood transfusion events per 100 patient years will be summarized by treatment group.
 
• The number of on-treatment RBC and whole blood transfusions per 100 patient years will be summarized by treatment group.
 
• The number of on-treatment RBC and whole blood units per 100 patient years will be summarized by treatment group.
 
• The reason for transfusion events will be summarized.
 
• The above summaries will be produced for the Evaluation Period and Week 52.
 
• An analysis of time to first RBC or whole blood transfusion will be performed as described in section 14.6.3, including a Kaplan-Meier plot.
 
• All transfusion summaries will be repeated for the primary definition of ESA hyporesponder subgroups (see Section 14.6.2).
 

CONFIDENTIAL

204837

*Dose Adjustment Scheme*

Endpoint / Variables

 
• Assigned dose by visit and at Day 1, Week 28, and Week 52
 
• Most recent dose prior to Week 28, Week 52 and end of study treatment
 
• Number (%) of participants with 0, 1, 2, or >2 dose adjustments during the following periods: 
 
○ Day 1 to < Week 28
 
○ Week 28 to ≤ Week 52
 
○ Day 1 to ≤ Week 52
 
 
 
• Number of dose adjustments during the following periods: 
 
○ Day 1 to < Week 28
 
○ Week 28 to ≤ Week 52
 
○ Day 1 to ≤ Week 52
 
 
 
• Number of dose adjustments per year during Day 1 to ≤ Week 52
 
• Time dose held for Hgb ≥12 g/dL
 

Planned Exploratory Displays

 
• The assigned dose by visit will be summarized using mean, standard deviation, minimum, P25, median, P75, and maximum by treatment group.
 
• The assigned dose by visit will also be summarized by treatment group using the number and percentage of subjects assigned to each dose level. Stacked bar graphs displaying assigned dose at all scheduled visits starting with Day 1 until Week 48 will be provided by treatment group.
 
• The median assigned dose by treatment and visit will be displayed graphically for each scheduled study visit using a line plot. The line plot of median assigned dose along with the first and the third quartiles by time will include vertical reference lines to identify the EP as well as the number of subjects by treatment group contributing to each median value.
 
• The number and percentage of patients with 0, 1, 2,....., 10 or > 10 dose adjustments will be summarized by treatment group. Summaries will be presented for the following categories of time: Day 1 – < Week 28, Week 28 – <= Week 52, and Day 1 – <= Week 52. This summary will be produced twice – the first time counting all dose adjustments, including adjustments related to periods of dose holds (i.e., no study treatment is given), the second time excluding dose adjustments related to periods of dose hold. The number and percentage of patients with dose adjustments by treatment group will also be summarized by Day 1 HemoCue Hemoglobin categories.
 
• The number of dose adjustments per subject will be summarized using mean, standard deviation, minimum, P25, median, P75, and maximum by treatment group. Summaries will be presented for the following categories of time: Day 1 – < Week 28, Week 28 – <=Week 52, and Day 1 – <= Week 52. For the period of time from Day 1 - <= Week 52, the number of dose adjustments per year will be summarized as well. This summary will be produced twice – the first time counting all dose adjustments, including adjustments related to periods of dose holds (i.e., no study treatment is given), the second time excluding dose adjustments related to periods of dose hold.
 
• The time (in days) that study treatment was withheld for HemoCue Hgb values ≥ 12 g/dL per subject will be summarized for all subjects and for subjects who had a dose hold using mean, standard deviation, minimum, P25, median, P75, and maximum by treatment group.
 

Summaries will be presented for the following categories of time: Day 1 – < Week 28, Week 28 – <=Week 52, and Day 1 – <= Week 52.

- Summary tables for the dose adjustment scheme endpoints will also be repeated for the following subgroups (see Section 5.4.2 for subgroup definitions):
  - rhEPO hyporesponders (primary definition)
  - Region
  - Race group
  - Baseline weight quartiles
- The median most recent dose by treatment and visit will be displayed graphically for each scheduled study visit using a line plot. The line plot of median most recent dose along with the first and the third quartiles by time will include vertical reference lines to identify the EP as well as the number of subjects by treatment group contributing to each median value. This plot will be created by treatment group and this plot will also be overlaid on a graph of corresponding Hgb values by visit.

